27 effects remain after the SHAM condition. If performance on naming RTs is +/- 1 standard  
28 deviation from the individual's benchmark mean, the REAL treatment condition will begin. If  
29 performance on naming RTs is > +/- 1 standard deviation from the individual's benchmark  
30 mean, REAL treatment will be postponed until the mean RTs fall within +/- 1 standard deviation  
31 of the benchmark. Periodic checks will be conducted weekly to identify when to begin REAL  
32 condition. Once there are minimal differences between naming RTs on the second word list,  
33 the REAL treatment will be initiated.

34

[figure not shown]
35 *Outcome measures:*

36 Two different word lists will be generated; a different list will be used for each treatment  
37 condition to control for exposure and learning effect. Pretreatment testing outcome measures will  
38 be recorded for 5 consecutive days for each outcome measure including: 1) naming accuracy 2)  
39 naming RTs on both word lists 3) performance on motor speech tasks and 4) performance on  
40 working memory tasks. Stability of baseline performance, defined as no more than 20%  
41 difference between scores, will be obtained in five consecutive sessions. In addition, outcome  
42 measures will be obtained immediately after each treatment session. Five maintenance  
43 outcome measures will also be obtained upon completion of treatment. These sessions will take  
44 place at the Clinical Translational Science Institute (CTSI) on [name] on the University  
45 of MN campus. An adverse events questionnaire will also be given after each treatment session  
46 as a mechanism of participants reporting any discomfort.

47  
48  
49

50

1 **Figure 1. Treatment Schedule**

6 *tDCS Protocol.*

7 Treatment sessions will take place at the University of MN Clinical Translational Science  
8 Institute. Each participant will be seated comfortably in a chair. A swim cap will be placed on  
9 the participant's head to identify cranial landmarks for accurate electrode placement. The area  
10 referred to as F3 by the International 10/20 system for electroencephalogram electrode  
11 placement has been established as the optimal location for targeting the left DLPFC.  
12 The F3 region will be located by marking the vertex (the midpoint between left and right tragus  
13 and midpoint between nasion and inion), measuring the head circumference. When these  

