14 measurements are entered into the Beam F3 Locator Software, additional values are provided  
15 to reliably identify the location of F3. Once F3 has been established, two saline soaked surface  
16 sponge electrodes (35cm) will be prepared and placed. For optimal anodal stimulation to the  
17 DLPFC, the anode will be placed over F3 and the cathode will be placed over the right  
18 supraorbital region. A current of 2mA will be delivered for 20 minutes  by a multichannel  
19 transcranial current stimulator (Starstim, Neuroelectrics Corporation; Cambridge, MA). a-tDCS  
20 will be applied before and during behavioral treatment in the design specified below.

25 *Behavioral-Based Naming Treatment Protocol.*

27 *Stimuli.* Eighty black-and-white line drawings will be obtained from on-line clip art websites.  
28 Picture names will be normed using five to ten English-speaking volunteers who will be asked to  
29 provide the names of the pictures. Cues words will be paired with the pictures if the words  
30 represent an associative or thematic relationship. Therefore, the words will be chosen that  
31 represent a concrete attribute (e.g., the picture, SHARK, is paired with the cue word *teeth*),  
32 location (e.g., the picture, SHARK, is paired with the cue word *ocean*), and either function or  
33 category (e.g., the picture, SHARK, is paired with the cue word, *fish*). The selection criteria for  
34 choosing these particular attributes is based on a classification criteria of thematic relations .  
35 Moreover, there is empirical evidence that that associative relations would prove beneficial in a  
36 naming treatment paradigm . Commonly used phrases (e.g., *great white shark*) or compound  
37 words (e.g., *bluefin shark*), synonyms or antonyms will be excluded. These cue words will be  
38 obtained from a semantic features normative database , which provides not only semantic

1 features information but categorical information as well. Two lists of 20-items will be created,  
2 which will be presented to each participant in order to avoid presenting the same list across the  
3 conditions. Pictures used in both lists will be balanced in terms of visual complexity and  
4 familiarity ratings. Words used in all conditions will be balanced in terms of lexical frequency  

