5 and word length. Familiarity ratings will be obtained from a normative database. Visual  
6 complexity ratings will be also obtained from a group of 20 individuals using the instructions and  
7 rating scales as reported in Snodgrass and Vanderwart's article. The CELEX database, will  
8 be consulted to determine lexical frequency of the words (cues) used in the study. An additional  
9 40 pictures will be selected for a control (untreated) list that will be used only during baseline  
10 and post-treatment testing. Performance on treated and untreated lists will be compared to  
11 determine treatment effects and possible generalization effects.

12  
13 *Naming Treatment Procedures.* All participants will be provided the same protocol, which will  
14 highlight the process of rehearsing the cues associated with the picture name. Treatment  
15 sessions will last until each participant has gone through the treated items twice. To insure  
16 control during the protocol, a graduate student trained in the protocol will administer the  
17 treatment steps. She will be blinded to the objectives of the study and conditions that are being  
18 administered. Treatment sessions will be video recorded for reliability purposes. To insure that  
19 she is not aware of when tDCS is being administered, a screen will be in place between the  
20 tDCS machine and the treatment table. The protocol is provided in Table 1.

21  
22 **Table 1. Naming Treatment Protocol.**

Steps Involved in Naming Treatment Protocol	
Picture Presentation	Participant will be asked to name the picture. If she/he is unable to provide the name within 10 seconds, the name will be provided.
Cue Presentation	Cues that accompany the picture will be presented. He/she will be asked to read each cue word as it is presented. If he/she is unable to read the word spontaneously within 10 seconds, he/she will be asked to repeat each word after the clinician.
Cue Rehearsal	Both picture and cues are taken away. Participant is asked to rehearse the cue words silently for 10 seconds.
Cue Self-Generation	Participant will be asked to generate all three cues. For each instance that the participant is unable to provide a cue within 10 seconds, the cues will be provided. Once the cues have been provided, the participant will then be asked to provide the picture name.

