26         • a diagnosis of moderate-moderately severe non-fluent aphasia based on  
27         performance on the WAB (see above screening procedures).  
28         • a diagnosis of moderate-moderately severe non-fluent aphasia based on  
29         performance on the BNT (see above screening procedures).  
30         • a diagnosis of mild-moderate apraxia of speech (AoS) based on performance on the  
31         ABA-2 (see above screening procedures).  
32         • completion of high school or GED  
33         • normal or corrected-to-normal vision  
34         • adequate hearing acuity for 1:1 conversational exchanges  
35         • use of English as primary language  
36         • a vascular lesion in the dominant left hemisphere, not in the region of the DLPFC  
37         verified by an MRI scan within six months of the start of the study.

38     These participants must also meet the following exclusionary criteria:

39  
40         • no previous history of neurological- or psychiatric-based illnesses or disease,  
41         language or learning disabilities, or alcohol/substance abuse  
42         • no history of seizures  
43         • no metal implants in the head (except dental fillings)  
44         • no lesion in the left DLPFC confirmed by MRI

1       • no current pregnancy

2  
3 Individuals who meet the inclusionary/exclusionary criteria and who are still interested in  
4 participating will then be consented to participate in the research study. After four  
5 participants have been identified as eligible and consented for the study, recruitment will  
6 stop.

7       • **Are statistical considerations, including sample size and justification, estimated  
8 accrual and duration, and statistical analysis clearly described and adequate to  
9 meet the study objectives?**

10  
11 Descriptive statistics such as naming percent accuracy, range of naming percent accuracy,  
12 number of cues generated independently, and rates of naming errors, will be collected. Although  
13 normally distributed data is not expected in this small sample size and in this population of  
14 participants, a Shapiro-Wilk test of normal distribution will be conducted to report the  
15 distribution. Single subject analysis techniques will be used such as visual inspection, graphical  
16 analysis and confidence interval comparison.

17  
18 *Aim 1.* To address the feasibility and safety aim, the number and type of adverse events for  

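### The SHAM and REAL word lists are balanced on norms only, so within a participant they can start at different levels and with different headroom; matching on that participant's own baseline is a cheap improvement

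*Combined protocol and SAP*

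**What the plan says.** All references are to the combined protocol and SAP.

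- *Stimuli*, on the treated lists: "Two lists of 20-items will be created". *Outcome measures* assigns a different list to each condition.
- *Stimuli*, on balancing: "Pictures used in both lists will be balanced in terms of visual complexity and" familiarity, and "Words used in all conditions will be balanced in terms of lexical frequency" and length. The sources lie outside the participant: "Familiarity ratings will be obtained from a normative database", and visual "complexity ratings will be also obtained from a group of 20 individuals using the instructions and" rating scales of a published article. CELEX is to "be consulted to determine lexical frequency of the words (cues) used in the study", so it is unclear whether the picture names themselves are matched on frequency.
- *Outcome measures*, on baseline: pre-treatment measures will "be recorded for 5 consecutive days for each outcome measure including: 1) naming accuracy 2") naming RTs, and so on. The reference to both word lists is attached to the RTs; for accuracy it is not explicit.
- Baseline has two stated uses. One is a stability rule (no more than 20% difference between scores). The other, in *Treatment Design*, is a post-washout check of RTs on the second list against their own earlier values.
- *Treatment Design* uses the SHAM-REAL order for everyone, and recruitment stops at four participants.
- The statistical section says: "Single subject analysis techniques will be used such as visual inspection, graphical" analysis and comparison of confidence intervals. Under Aim 2, naming accuracy is summarised by a d statistic read against benchmarks of 4.0, 7.0 and 10.1.

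No section assigns pictures by a participant's own naming, compares the two lists at baseline, or sets a tolerance for a gap.

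**The concern.** Which pictures a person with aphasia can name is partly individual, and norms from other people capture only part of it. Two lists balanced on norms can therefore be unequal for a given participant. Since list is tied to condition and the analysis is per subject, such a gap is not averaged out. Rotating lists over conditions would average it over people but would leave each person's own comparison unbalanced.

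Change from baseline removes the difference in starting level. It does not remove the difference in headroom: a list that starts higher has fewer pictures left to learn. If gain depends on headroom, the two conditions show different gains with no difference in stimulation effect.

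The existing checks do not cover this. Two lists can each be stable at different levels, and the washout check compares the second list with itself, on RT only.

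**Working it through.** The plan states no figure on this point, so there is none to reproduce. The checks below illustrate mechanism and size.

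**1. Mechanism.** Assume a share g of the unnamed pictures is acquired in either condition: gain = g × (20 − baseline).

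- Baselines 6 and 8, g = 0.5: gains 0.5 × 14 = 7 and 0.5 × 12 = 6.
- Baselines 6 and 10, g = 0.5: gains 7 and 0.5 × 10 = 5. At an assumed baseline SD of 1 picture, d = 7.0 (the medium benchmark) and 5.0 (small), with no true difference between conditions. A four-picture gap is uncommon; this pair shows direction, not typical size.

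**2. Size.** From the documents: 20 pictures per list, five baseline days, four participants. Assumed: item logits normal with mean −0.5 and SD 1 to 2 within a person (mean accuracy about 40 to 42%), norms explaining 0 to 50% of item variance, and 60% of each item's headroom closed in both conditions.

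- Item probability: p = 1 / (1 + exp(−logit)).
- True starting gap: D = Σp (list 1) − Σp (list 2).
- Spurious gain difference: 0.6 × Σ(1−p) over list 1 minus the same over list 2 = −0.6 × D, so its SD is 0.6 × SD(D).
- Chance in at least one of four people: 1 − (1 − q)⁴, where q is the chance per person.

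Simulated results:

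| Item SD | Share explained by norms | SD of starting gap | SD of spurious gain difference | Spurious gain difference of 2 or more, at least one of four |
|---|---|---|---|---|
| 2 | 0% | 1.9 | 1.2 | 31% |
| 2 | 50% | 1.4 | 0.85 | 7 to 8% |
| 1 | 0% | 1.3 | 0.8 | 3% |
| 1 | 50% | 0.9 | 0.55 | about 0% |
| 1 to 2, own-baseline pairs | any | 0.9 to 1.0 | 0.55 to 0.6 | close to 0% |

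For the first row, q is about 9% (0.089), and 1 − 0.911⁴ = 0.31.

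**3. Total variability.** Add binomial sampling to five-session means before and after treatment. Under norm balancing, the observed REAL-SHAM gain difference has SD about 1.8 to 2.0 pictures. If the five-day baseline used for pairing is also the analysis baseline, the SD falls to 1.2 to 1.3, because pairing makes the two observed baselines nearly equal. If the analysis baseline were an independent re-measurement, the fall would be only from 1.97 to 1.69 (1 − 1.69/1.97 = 14%) with norms at 0%, or from 1.80 to 1.69 (6%) with norms at 50%, both at item SD 2.

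**The case against.** The plan does control list difficulty, on four properties. Its stated primary purpose is feasibility and safety. Aim 2 is a four-person exploration read by visual inspection and confidence intervals, without a hypothesis test. The headroom artefact is smaller than ordinary session noise (SD about 1.6 pictures at item SD 2). It needs gain to rise with headroom: if gains were a fixed number of pictures below ceiling, it would be zero. At item SD 1 with norms explaining half the variance, own-baseline pairing barely changes it. All of this stands, and it limits the weight of the point.

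Three stronger readings are not supported.

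- A reader might infer that most trials of this kind would be misled, because at item SD 2 at least one of four participants has a starting gap of 2 or more pictures in 76% to 49% of trials. That figure concerns starting level, which change from baseline removes. The relevant figures are those for gain.
- A reader might infer a bias in favour of REAL. Nothing in the documents gives the gap a direction.
- A reader might take it as settled that accuracy on all 40 pictures is known before training. The text says so for RT only; for accuracy it is a reasonable reading that needs confirming.

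The objection does not show that any existing rule detects or limits a gap between lists within a person.

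**Conclusion.** The point holds as a cheap improvement, not as a flaw that invalidates the comparison. The lists are balanced on norms only, each list is tied to one condition, and a within-person gap in headroom passes into the per-subject REAL-SHAM comparison with unknown sign.

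Its size rests on assumed accuracy, item variance, norm share and headroom closure. Within the range shown it runs from negligible to moderate. The gain in precision is steadier over that range, but the full reduction requires that the pre-SHAM five-day baseline also be the analysis baseline. The plan does not say which baseline enters the accuracy effect size for REAL. The size for RT was not modelled.

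**What to change.** In *Outcome measures* and *Stimuli*:

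1. State that accuracy as well as RT is recorded, picture by picture, on all 40 trained-pool pictures on the five pre-SHAM days.
2. After the last baseline day and before any item is trained, rank the 40 pictures by that participant's number correct out of five. Break ties by a normed property such as lexical frequency or familiarity. RT will not serve: it is undefined for pictures never named correctly (about 26% of items in the model at item SD 2).
3. Pair neighbours, and randomly assign one of each pair to SHAM and the other to REAL.
4. Redraw if the normed properties differ by more than a tolerance set in advance.
5. Report each list's baseline accuracy and RT per participant, and state which baseline enters the effect size.

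The cost is a short script per participant between baseline and the first SHAM session. If accuracy is already meant to cover both lists, no extra testing is needed. The washout check can still be run, with the second-list benchmark computed from the same baseline days once the lists are formed. The downside is small: lists differ between participants, which matters little in a within-person analysis. The fixed SHAM-REAL order remains a separate confound.

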46    relationship to emotional well-being and functional communication, treatment that  
47    improves naming deficits will positively influence quality of life in many of these individuals.  
48    The approach taken to remediate naming deficits in aphasia is to treat impaired WM systems

1 on the premise that certain cognitive processes underlie linguistic functions in aphasia. This  
2 approach represents a departure from most behavioral-based naming treatment approaches,  
3 but reflects a growing recognition that WM systems in individuals with aphasia impact  
4 linguistic performance . The addition of a-tDCS as a neuromodulation tool to increase  
5 cortical excitability (upregulate) the working memory center to target naming is a novel  
6 approach in aphasia. These findings, , will provide valuable information regarding the role  
7 WM plays in naming and the potential benefit of using neuromodulation to the DLPFC to  
8 influence naming in aphasia.

9

- 10 • **Is the design of the study appropriate for the questions that are posed?**

11

12 *Treatment Design:*

13 A single subject cross-over design with a 4 week wash out period will be used. Two treatment  
14 conditions will be presented. The sham (SHAM) condition will consist of presentation of sham  
15 tDCS for 20 minutes followed by behavioral naming treatment. The real treatment condition  
16 (REAL) will consist of 20 minutes of a-tDCS to the left DLPFC followed by behavioral naming  
17 treatment. The length of behavioral naming treatment will depend on how long each participant  
18 takes to go through the treatment stimuli twice. A SHAM-REAL sequence will be used across all  
19 participants. Although order effects may be introduced using the same sequence across  
20 participants, the small number of participants makes it difficult to interpret any data that comes  
21 from using a counterbalanced presentation of treatment.

22 Treatment will be provided over five consecutive days. A minimum of a one-month washout  
23 period will be provided between the two conditions (Figure 1). Prior to initiating the REAL  
24 treatment condition, the naming RTs obtained on the second word list during the pre-treatment  
25 testing period (prior to the initiation of the SHAM condition) will be compared to the naming RTs  
26 obtained after the washout period. RTs will be analyzed to ensure that no lasting treatment  

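### With no minimum time since stroke, a fixed SHAM-REAL order and no described accuracy re-test before REAL, spontaneous recovery can be credited to real stimulation

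*Combined protocol and SAP*

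**What the plan says.** **Eligibility.** The inclusionary criteria require a left-hemisphere vascular lesion outside the DLPFC, "verified by an MRI scan within six months of the start of the study". Neither list sets a time since stroke. Recruitment stops at four participants.

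**Order and timing.** Under Treatment Design, "A SHAM-REAL sequence will be used across all" participants. The plan concedes that this may introduce order effects and keeps the order because the sample is small. On duration: "Treatment will be provided over five consecutive days. A minimum of a one-month washout" separates the two conditions.

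**Check before REAL.** The plan compares "treatment condition, the naming RTs obtained on the second word list during the pre-treatment" period with those obtained after the washout, and places that period before SHAM starts. REAL is postponed, with weekly re-checks, while mean reaction time lies more than 1 SD from the individual's benchmark. No re-test of accuracy, working memory or motor speech is described at this point.

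**Baseline.** Under Outcome measures, accuracy is recorded on five consecutive pre-treatment days, with a 20% limit on differences between scores as the stability rule. The mention of both lists is attached to reaction time, not to accuracy.

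**Lists and analysis.** Each condition has its own 20-item list. A separate set of 40 untreated pictures is tested at baseline and after treatment, to judge treatment effects and generalization. Accuracy is analysed as a standardised effect size against benchmarks of 4.0, 7.0 and 10.1. The plan does not say which baseline the REAL effect size uses.

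**The concern.** The six-month limit is easily taken for a chronicity criterion, but it constrains only the scan. A participant with a recent stroke can be enrolled, and hospitals are among the recruitment sources.

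Such a participant may improve without any treatment. If both conditions' accuracy gains are measured from the same pre-SHAM testing, REAL collects several more weeks of that improvement than SHAM does. Hypothesis 2 predicts gains after REAL and not after SHAM, so the artefact points the same way as the hypothesis. Aim 2 also uses these data to set the sample size of future studies. With four participants, one who is still recovering could distort the effect carried forward.

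**Working it through.** The plan gives no expected effect, power or sample size calculation, so there is no figure of its own to reproduce. What follows illustrates size only.

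**Inputs from the plan:** five baseline days, five treatment days per condition, a washout of four weeks (elsewhere at least one month), 20 items per treated list, small benchmark 4.0.

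**Assumptions, not in the documents:**
- The washout is 28 days; a longer one lengthens the REAL lag.
- SHAM starts the day after baseline, or after a weekend gap.
- The outcome is the last treatment day.
- Recovery is linear at 0.1, 0.2 or 0.4 items per week (0.5, 1 or 2 percentage points of 20 items).
- Session-to-session baseline SD is 0.5, 1 or 2 items.
- There is no treatment effect.
- The effect size is d = (post - baseline mean) / baseline SD.

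**Step 1: lags from mid-baseline (day 3).**
- No gap: SHAM ends on day 10, a lag of 10 - 3 = 7 days. REAL runs from day 39 (10 + 28 + 1) to day 43, a lag of 40 days.
- Weekend gap: SHAM ends on day 12, a lag of 9 days. REAL ends on day 45, a lag of 42 days.
- The extra lag for REAL is 33 days either way, or 33/7 = 4.7 weeks.

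**Step 2: extra gain for REAL.** Rate x 4.7 weeks gives 0.47, 0.94 and 1.89 items, or 2.4, 4.7 and 9.4 percentage points.

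**Step 3: spurious d = rate x (lag / 7) / SD.**

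| Recovery (items/week) | SHAM d, SD 1 | REAL d, SD 1 | REAL d, SD 0.5 | REAL d, SD 2 |
|---|---|---|---|---|
| 0.1 | 0.10-0.13 | 0.57-0.60 | 1.14-1.20 | 0.29-0.30 |
| 0.2 | 0.20-0.26 | 1.14-1.20 | 2.29-2.40 | 0.57-0.60 |
| 0.4 | 0.40-0.51 | 2.29-2.40 | 4.57-4.80 | 1.14-1.20 |

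**Step 4: recovery needed for REAL to reach 4.0.** Rate = 4.0 x SD / (lag / 7):
- SD 0.5: 0.33-0.35 items per week
- SD 1: 0.67-0.70
- SD 2: 1.33-1.40

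**Step 5: would the stability rule catch it?** From the first to the fifth baseline day is 4 days. At 0.4 items per week the score moves 0.4 x 4/7 = 0.23 items (1.1 points). Even at 1 item per week it moves 0.57 items (2.9 points). Read as percentage points, the 20% limit is 4 of 20 items, so slow drift passes.

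**Step 6: effect of a new reference before REAL.** A five-day re-baseline would give REAL the same 7-9 day lag as SHAM. At 0.4 items per week and SD 1, spurious REAL d falls from 2.3-2.4 to 0.4-0.5. A single check the day before REAL leaves 5 days, so 0.4 x 5/7 = 0.29.

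**The case against.** **The pre-SHAM accuracy baseline is an inference.** A reader might take it as stated that REAL accuracy is measured from before SHAM. The text does not say so: it ties both lists to reaction time only, names no baseline for the effect size, and the schedule in Figure 1 is not available here. With a fresh accuracy baseline before REAL, steady recovery would add about equally to both conditions. This stands, and the point is conditional on it. Still, the text describes pre-SHAM accuracy testing and no later accuracy baseline.

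**Bias in every participant.** A reader might infer this from the fixed order. It does not follow, because the participant must still be recovering. Support groups are also a recruitment source, and nothing shows that anyone enrolled would have had a recent stroke.

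**Bias beyond the reach of analysis.** A reader might infer this too from the unvarying sequence. The 40 untreated pictures argue against it, since general recovery should raise them as well and a treated-minus-untreated contrast could remove much of it. What remains is that the plan gives no rule for that subtraction, so a gain on untreated items may be read as generalization.

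**The reaction-time check.** It would hold back a participant whose naming speed had moved by more than 1 SD. That is a partial safeguard, but it does not cover accuracy, and each postponement lengthens the REAL lag.

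**Order effects are already acknowledged.** True, but the acknowledgement deals with neither time since stroke nor the missing accuracy re-test.

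**Conclusion.** The point holds in conditional form. The absence of a time-since-stroke criterion, the fixed order and the absence of any described accuracy re-test before REAL are plain in the text. If a participant is still recovering and the REAL accuracy effect is taken from the pre-SHAM baseline, recovery can be credited to REAL over a lag of about 40-42 days against 7-9 for SHAM.

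The direction follows from the design; the size does not. It rests on assumed recovery rates and SDs. At 0.1-0.4 items per week and SD 1, spurious REAL d is about 0.6-2.4, below the small benchmark. Within that range of rates it exceeds 4.0 only at the top rate with an SD near 0.5. A reader might infer that recovery alone would produce a benchmark-sized effect, but the documents give no figures to support that. This should be changed, mainly because the remedy is cheap.

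**What to change.** 1. Add a minimum time since stroke to the inclusion list, with the value set by the investigators, and report time since stroke for each participant.
2. At the post-washout check or checks, score accuracy as well as reaction time on the second list, and use that level as the reference for the REAL accuracy gain. One check gives no SD, so take the SD for d from the five-session pre-treatment baseline. State in the analysis section which reference and which SD are used.
3. Pre-specify the treated-minus-untreated change in each condition as the check on recovery, using the control list already collected. Compute both parts over the same interval, and confirm that the control list is tested after each condition. This contrast also subtracts any true generalization, so report the untreated change alongside it.

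**Cost.** One eligibility line, scoring of responses already elicited, and a few sentences of analysis text. The pool for four places becomes slightly narrower. The REAL reference is less precise: with independent sessions, one session has a standard error of 1 SD, against SD/√5 = 0.45 SD for five. Averaging several checks, where they occur, narrows that gap.
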